Thus, we will enroll between 100-200 participants in total. There may be overlap in the Protocol A and Protocol B participants. As previously stated, participants will be given the opportunity (optional) to participate in both Protocols A and B. (Thus, in the event that all participants complete both protocols, we will enroll only 100 total participants, i.e., 50 patients and 50 healthy controls).

This being the first study of its kind, it is difficult to do a formal power and sample size

analysis because we do not have a measure of effect size, but given previous similar studies and our usual rate of loss to follow up, we calculate we will need 50 participants per group for each protocol.

Our enrollment numbers take into account the likelihood of attrition. We will only be able to use data sets that are complete (i.e., data collected from sham, excitatory, and inhibitory TMS). However, we anticipate that a subset of enrolled participants will not be able to complete all three study visits within a protocol because of scheduling or other challenges. Though we aim to enroll up to 50 patients and 50 healthy controls per protocol, we expect that the number of participants on whom we have useable data will be smaller.

Inclusion Criteria:

Patients

- Men and women
- Ages 18-50 years
- Patients diagnosed with schizophrenia (SZ), schizoaffective disorder (SZA), or psychotic bipolar disorder (BP).
- On a stable psychiatric medication regimen for at least a month prior to and during study participation
- Have structural brain MRI data on file from previous participation in research within the McLean Hospital Schizophrenia and Bipolar Disorder Program
- Have clinical diagnostic data (Structured Clinical Interview for DSM-IV: SCID) on file from previous participation in research within the McLean Hospital Schizophrenia and Bipolar Disorder Program

Healthy Controls:

- Men and women
- Ages 18-50 years
- Without major psychiatric illness
- Have structural brain MRI data on file from previous participation in research within the McLean Hospital Schizophrenia and Bipolar Disorder Program

Exclusion Criteria:

Patients

- Any change in psychiatric medications within a month prior to and during study participation
- Legal or mental incompetency
- Intellectual disability
- Substance use disorder (abuse or dependence) with active use within the last 3 months
- Significant medical or neurological illness
- Prior neurosurgical procedure
- History of seizures

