As a means of assessing participants' understanding of what the study entails, we will conduct a one-on-one informed consent survey, which asks questions such as, "What illness is being studied in this project?" "Are there any risks to participating in this study?" and "Will you lose any of your benefits if you refuse to participate in this study?" If the participant is unable to answer the questions or demonstrates a lack of understanding, the investigator will review the details of the study again. The survey therefore serves to ensure that participants are actively engaged in the informed consent process. For each participant, we will re-administer the informed consent survey at the beginning of each visit, in order to ensure that the participant is capable of consent throughout the entire study. Participants who are unable to answer all 9 questions on the survey correctly even after additional information is provided will be excluded from the study.

We will acquire written informed consent for all participants using the IRB-approved consent form. All signed forms will be stored in a file cabinet in a locked office.

For individuals who wish to participate in the second protocol (e.g., Protocol B after completing Protocol A), we will take the necessary time to remind participants about the study procedures, risks, and benefits, and answer any questions they may have about the study. We will also re-evaluate whether participants continue to meet the eligibility criteria. However, because Protocols A and B are both part of this same IRB protocol, we will not maintain separate written informed consent forms for the two protocols.

Treatment assignment, and randomization

All subjects, including controls, will receive either cTBS (inhibitory), iTBS (excitatory), or sham TBS in each of the three visits. The order in which they receive a particular type of TMS will be randomized for each subject by the study staff prior to the first TMS administration. The investigators and the research coordinator will not be blinded to the randomized order, since all

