As part of the clinical evaluation, we will also ask female participants about and record the first date of their last menstrual period (LMP). Clinical symptoms and cognitive functioning can vary according to the phase of the menstrual period. We will evaluate what phase of the menstrual cycle a female participant is in at the time of each study visit so that we can potentially control for any associated confounding effects.

Similarly, nicotine is well-documented to affect cognitive functioning, and is an important variable to control for. Therefore, we will administer a Fagerstrom Test for Nicotine Dependence in all research participants. For individuals who are smokers, we will record the time of the participant's last cigarette prior to each study visit.

For all subjects, during each and every visit, urine toxicology screens will be used to assess for current substance use, and urine pregnancy tests in women of child-bearing age to determine if she is

pregnant (and thus is ineligible to participate in the study).

Scheduling of study visits

As mentioned before, this will be a cross-over design, in which participants will undergo excitatory, inhibitory, and sham TBS over three study visits, separated by at least 36 hours. The order in which participants receive excitatory vs. inhibitory vs. sham TMS will be randomized.

The effects of a single session of rTMS are acute and reversible, and usually recede in less than an hour. Nonetheless, the study visits will be separated by at least 36 hours in order to provide more than ample time for the brain to return to homeostatic balance and ensure that there are no potential residual TMS effects from the previous study visit.

If scheduling permits, participants may be able to complete all three study visits in as short as one week. However, to accommodate scheduling flexibility for research participants, we will allow up to two months for participants to complete all three study visits within a single protocol.

Participants will participate in one of two protocols, Protocol A (**Figure 2**) or Protocol B (**Figure 3**). The two protocols are identical except that they involve different time perception and executive function tasks. Specifically, the tasks in Protocol A are the interval discrimination task, flanker task and the N-back working memory task, while those in Protocol B are the repetitive finger tapping task and the multi-source interference task (MSIT).

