We will test for group differences in demographic and clinical variables using SPSS, using χ^2 and t-tests for ANOVA as appropriate. We will first measure the change (Δ) in each of the pre- and post-TMS assessments at each study visit: i.e. accuracy in time interval discrimination task, accuracy and reaction time (RT) in N-back working memory task, executive function in Flanker task accuracy and RT in repetitive finger tapping task, and accuracy and RT in MSIT. We will then run two-way ANOVA for each outcome measure, with diagnosis (patients vs. healthy controls) and the TMS type (excitatory, inhibitory, or sham) as independent variables. These models will include as covariates sex, age, handedness, medication load, and symptom severities (derived from the clinical scales scores: NAART, PANSS, YMRS, MADRS, PSYRATS, BRIEF-A, BIS-11, and the Fagerstrom Test).

D. Power analysis (e.g. sample size, evaluable subjects)

This is a pilot study. This being the first study of its kind, it is difficult to do a formal power and sample size analysis because we do not have a measure of effect size, but given previous similar studies and our usual rate of loss to follow up, we estimate we will need 50 participants per group for each protocol. Of primary interest to the study is the change (Δ) in outcome measures within the psychosis group. With 50 subjects in the psychosis group, we will have 80% power to detect an effect size of 0.35, which is a moderate effect.

VII. RISKS AND DISCOMFORTS:

Common risks of TMS procedure

Subject may feel twitching of the scalp muscles during stimulation and/or local discomfort (tapping sensation) under the coil. It is possible that the subject may feel a headache after the TMS measurement that is generally caused by keeping the head in the same position for a lengthy period of time and/or by stimulation of the scalp muscles and nerves by the TMS pulses. TMS may also induce nausea in some patients¹¹⁴. The headache or nausea, if present, is typically mild, disappears soon and can be treated by mild over-the-counter analgesics.

Although there are no reports suggesting increased risk for TMS during pregnancy, pregnant women are excluded from this study due to insufficient knowledge of the effects of the strong magnetic fields on the fetus.

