PROTOCOL TITLE

Cerebellar transcranial magnetic stimulation (TMS) in psychotic disorders: effect on time perception, executive function, and mood and psychotic symptoms

NCT Number: NCT02642029

Date: August 22, 2022

Statistical Analyses:

We will test for group differences in demographic and clinical variables using χ^2 and t-tests or ANOVA, as appropriate. To examine the effect of TBS conditions on symptoms (as measured by visual analog scale scores, which are not normally distributed), we will conduct the non-parametric Friedman's test. For all other outcome measures, we will use mixed model regressions with TMS condition (cTBS, iTBS, or sham TBS), time (pre-TMS, post-TMS), and the interaction of condition x time as the primary variables of interest. To test the association between performance on the interval discrimination task (IDT) and symptoms, we will run mixed model regression models with TMS condition and time in addition to symptom score as the primary variable of interest.

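### Protocol VI.C's two-way ANOVA has no participant term, yet it is the only written diagnosis and diagnosis × TMS analysis of the task outcomes, because the SAP's mixed model omits diagnosis

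*Protocol*

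**What the plan says.** Protocol VI.C starts from per-visit differences: "We will first measure the change (Δ) in each of the pre- and post-TMS assessments at each study visit". It continues: "We will then run two-way ANOVA for each outcome measure, with diagnosis (patients vs. healthy controls) and the TMS type" as independent variables, plus covariates. The covariates are person-level characteristics and clinical scores. No participant effect, repeated factor or error stratum is named.

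The design makes TMS type a within-person factor. Section IV (randomization) says "All subjects, including controls, will receive either cTBS (inhibitory), iTBS (excitatory), or sham TBS in each of the three visits", and Section V (scheduling) confirms that "participants will undergo excitatory, inhibitory, and sham TBS over three study visits, separated by at least 36 hours". Section III restricts the analysis further: "We will only be able to use data sets that are complete (i.e., data collected from sham, excitatory, and inhibitory TMS"). Every analysed person therefore has three change scores per outcome.

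The SAP, dated August 22, 2022, describes a different analysis. For the symptom scales, "we will conduct the non-parametric Friedman's test". Then: "For all other outcome measures, we will use mixed model regressions with TMS condition", time and their interaction as the terms of interest. It does not write out random effects, includes no diagnosis term, and does not say whether it replaces VI.C. Its one sentence on group differences covers demographic and clinical variables only.

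**The concern.** Diagnosis varies between people and TMS type varies within people, yet VI.C lists them in the same way. A two-way ANOVA with no participant term uses one pooled error for both. If people differ consistently in how much they change from pre to post, that error is too small for the diagnosis comparison, because three scores from one person count as three people. It is too large for the TMS and diagnosis × TMS comparisons, because variation between people stays in it. The two errors run in opposite directions.

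The SAP's mixed model deals with the TMS contrasts but leaves diagnosis out. Patient-control comparisons are part of Aim 1, and VI.C makes diagnosis a factor for every task outcome. The one written plan for those tests is thus the one whose error term is in doubt.

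**Working it through.** **1. The plan's own figure.** Section VI.D gives 80% power for an effect size of 0.35 with 50 patients. A one-sample test on change has 0.35 × √50 = 2.475. One-sided at 0.05: Φ(2.475 − 1.645) = 79.7%. Two-sided: Φ(2.475 − 1.960) = 69.7%. The figure reproduces as a one-sided test of within-group change (sidedness is not stated). It says nothing about the two-way ANOVA and does not bear on this point.

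**2. Inputs.** 50 patients and 50 controls per protocol (Sections III and VI.D); three change scores each, so up to 300 values (Sections III to V and VI.C). Assumed: nominal α of 5%, and the correlation ρ between one person's change scores, which the documents do not give. A range is shown.

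**3. Formulas.** Let a change score have variance σ². With no participant term, the error mean square estimates σ² on 300 − 6 = 294 degrees of freedom.

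- Diagnosis: a person's mean of three scores has variance σ²(1 + 2ρ)/3, but the model assumes σ²/3. True size = 2{1 − Φ(1.96/√(1 + 2ρ))}.
- Diagnosis × TMS (2 df; the TMS main effect is the same): within-person contrasts carry σ²(1 − ρ), but the model assumes σ². True size = P(χ² on 2 df > 5.99/(1 − ρ)) = exp{−2.996/(1 − ρ)}.

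**4. Results at nominal 5%.**

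| ρ | 1.96/√(1+2ρ) | Diagnosis size | Simulated | 2.996/(1−ρ) | Diagnosis × TMS size | Simulated |
|---|---|---|---|---|---|---|
| 0 | 1.960 | 5.0% | 5.0% | 2.996 | 5.0% | 4.9% |
| 0.1 | 1.789 | 7.4% | 7.5% | 3.329 | 3.6% | 3.5% |
| 0.3 | 1.550 | 12.1% | 12.1% | 4.280 | 1.4% | 1.5% |
| 0.5 | 1.386 | 16.6% | 16.5% | 5.992 | 0.25% | 0.25% |

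The simulation used 40,000 runs per ρ, 50 per group, and no covariates. With a participant term added, all three tests stayed at 4.9% to 5.1% for every ρ tried from 0 to 0.7.

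**5. What ρ requires.** A person's stable level cancels from a pre-to-post difference, so under a pure random-intercept model ρ = 0. If people differ in their change with variance s², and a single score has residual variance e², then ρ = s²/(s² + 2e²), so s²/e² = 2ρ/(1 − ρ). That is 0.2/0.9 = 0.22, 0.6/0.7 = 0.86 and 1/0.5 = 2 at ρ = 0.1, 0.3 and 0.5.

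**6. TMS power, relevant only if VI.C governs.** For a 0.35 SD shift in one condition with 100 people, power with and without a participant term is 72% and 72% at ρ = 0, 87% and 73% at ρ = 0.3, and 96% and 75% at ρ = 0.5 (20,000 runs each).

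**The case against.** A reader might infer that the trial will certainly analyse 300 correlated values as independent, and that both the diagnosis and TMS results will be wrong. The documents do not support that, for four reasons.

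- VI.C does not say that the ANOVA is between-subjects. The study is described as a crossover and restricted to complete data sets, which suits a repeated-measures ANOVA. This stands: the defect is that the text names no such term, not that it rules one out. If one was intended, the wording still has to change.
- The SAP already assigns every task outcome to a mixed model and the symptom scales to Friedman's test, both methods for repeated data. This stands for the TMS contrasts, subject to the random effects being written out. It does not reach diagnosis, which the SAP model lacks.
- The inflated test is the diagnosis main effect on change averaged over the three TMS types. Aim 1 instead compares patients' and controls' performance at baseline and after sham, and predicts opposite changes in patients after excitatory and inhibitory TMS, which would tend to cancel in that average. The interaction is nearer the aims, and there the error is conservative. This stands and limits the harm. It also shows that neither document writes out a model for the Aim 1 level comparisons.
- No ρ is given, and it may be near zero. VI.C's person-level covariates could absorb part of it, and the simulation omits them. This stands: the table is a range, not an estimate. Having fewer completers than 50 per group matters little, since the size formulas do not involve the sample size.

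**Conclusion.** The point holds in a limited form. VI.C's ANOVA names no participant term, and it is the only written analysis of diagnosis and diagnosis × TMS for the task outcomes. If it is run as literally written, and change scores correlate positively within a person, the diagnosis main-effect test is anti-conservative (about 7%, 12% and 17% at ρ = 0.1, 0.3 and 0.5). The diagnosis × TMS test is then over-conservative (about 3.6%, 1.4% and 0.25%). At ρ = 0 neither test is wrong. The sizes assume equal correlation between the three scores and no covariates.

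The loss of TMS power should not be counted against the plan unless VI.C rather than the SAP governs. Severity is moderate: the study is a pilot, Section VI.D puts the primary interest in change within the psychosis group, and the inflated test is not the comparison that Aim 1 hypothesises.

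**What to change.** - State in the SAP that its mixed model replaces the VI.C ANOVA.
- Add diagnosis, diagnosis × condition, diagnosis × time and diagnosis × condition × time to that model.
- Write out the random effects: a participant intercept and, since pre and post scores are modelled, a visit-within-participant intercept. Both cancel from the pre-to-post change, so a participant × time term is also needed to put diagnosis × time against between-participant error. Fitting the change scores with a participant random intercept does the same job for the change comparisons.
- Test diagnosis against between-participant error, and write out the Aim 1 patient-control contrasts at baseline and after sham.

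The cost is a few sentences in VI.C and the SAP. The data do not change, and little is lost if ρ proves to be zero: in the simulation at ρ = 0, TMS power was 72% with or without the participant term.

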- History of ECT treatment or clinical TMS within the past three months
- History of participation in a *cerebellar* TMS study
- Implanted cardiac pacemakers
- Patients who have conductive, ferromagnetic or other magnetic-sensitive metals implanted in their head or neck, or are non-removable and within 30 cm of the treatment coil. These include:
 - Aneurysm clips or coils
 - Carotid or cerebral stents
 - Metallic devices implanted in the head (e.g. Implanted pacemaker, medication

- pump, vagal stimulator, deep brain stimulator, TENS unit, or ventriculo-peritoneal shunt)
 - Magnetically active dental implants
 - Cochlear/otologic implants
 - CSF shunts
 - Ferromagnetic ocular implants
 - Pellets, bullets, fragments less than 30 cm from the coil
 - Facial tattoos with metallic ink, permanent makeup less than 30 cm from the coil
- Pregnant women

Healthy Controls:

- History of major psychiatric illness, including psychosis
- Has a first-degree relative with psychosis
- Active use of neuropsychoactive medications
- Legal or mental incompetency
- Intellectual disability
- Substance use disorder (abuse or dependence) with active use within the last 3 months
- Significant medical or neurological illness
- Prior neurosurgical procedure
- History of seizures
- History of ECT treatment or clinical TMS within the past three months
- History of participation in a *cerebellar* TMS study
- Implanted cardiac pacemakers
- Individuals who have conductive, ferromagnetic or other magnetic-sensitive metals implanted in their head or neck, or are non-removable and within 30 cm of the treatment coil. These include:
 - Aneurysm clips or coils
 - Carotid or cerebral stents
 - Metallic devices implanted in the head (e.g. Implanted pacemaker, medication pump, vagal stimulator, deep brain stimulator, TENS unit, or ventriculo-peritoneal shunt)
 - Magnetically active dental implants
 - Cochlear/otologic implants
 - CSF shunts
 - Ferromagnetic ocular implants
 - Pellets, bullets, fragments less than 30 cm from the coil
 - Facial tattoos with metallic ink, permanent makeup less than 30 cm from the coil
- Pregnant women

Source of subjects and recruitment methods

For patients, we will preferentially, though not exclusively, recruit individuals who are already enrolled in one of two ongoing research studies in the McLean Hospital Schizophrenia and Bipolar Disorder Program:

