 - N-back working memory task for Protocol A (or multi-source interference task (MSIT) for Protocol B)
 - Flanker task for Protocol A
 - Visual analog scales (VAS) to assess mood and psychotic symptoms

Healthy Control Participants:

- Consenting procedures (15-20 minutes)
- Clinical characterization (1-2 hours)
 - Structured Clinical Interview for DSM-IV-TR (SCID)
 - North American Adult Reading Test (NAART)
 - The Behavior Rating Inventory of Executive Function – Adult Form (BRIEF-A)
 - Barratt Impulsiveness Scale (Version 11; "BIS-11")
 - Fagerstrom Test for Nicotine Dependence
- Urine toxicology/pregnancy screen (5 minutes)
- Baseline/pre-TMS assessments (15-20 minutes)
 - Interval discrimination task for Protocol A (or repetitive finger-tapping task for Protocol B)
 - N-back working memory task for Protocol A (or multi-source interference task (MSIT) for Protocol B)
 - Flanker task for Protocol A
 - Visual analog scales (VAS) to assess mood and psychotic symptoms
- Transcranial Magnetic Stimulation (TMS) (15 minutes)
- Visual analog scales (VAS) to assess mood and psychotic symptoms
 - Excitatory, inhibitory, or sham (order randomized)
- Post-TMS assessments (15-20 minutes)
 - Interval discrimination task for Protocol A (or repetitive finger-tapping task for Protocol B)
 - N-back working memory task for Protocol A (or multi-source interference task (MSIT) for Protocol B)
 - Flanker task for Protocol A
 - Visual analog scales (VAS) to assess mood and psychotic symptoms

Clinical characterization

For the purposes of clinical characterization, we will record demographic (i.e. age, sex, race/ethnicity, parental education, duration of illness, handedness) and medication information for all subjects during the first visit. For healthy control participants, we will administer the SCID, which assesses lifetime history of psychiatric symptoms and diagnoses, but not symptom severity, which can fluctuate over time. To capture the clinical presentation of patients at the time of the study, we will use the following clinical scales (included with this protocol): PANSS, YMRS, MADRS, PSYRATS-AH, BRIEF-A, BIS-11. Each of these scales will be used to capture the most severe symptoms in the previous month. The NAART, BRIEF-A, BIS-11, will be administered for all subjects. The clinical characterization step will not be repeated at study Visits 2 and 3 for either Protocol A or B.

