Should they choose to do so, participants may optionally return to participate in the protocol in which they have not already participated (e.g., Protocol B after completing Protocol A) at any time point that the study remains open to recruitment and the participant continues to meet eligibility criteria. Once a participant returns for Visit 1 of the second protocol, we will allow up to two months for participants to complete study Visits 2 and Visits 3 of the same protocol.

Figure 2. Protocol A

Visit 1		Visit 2		Visit 3
NAART*				
PANSS				
YMRS				
MADRS				
PSYRATS-AH				
BRIEF-A*				
BIS-11*				
Fagerstrom*				
Utox and upreg screens		Utox and upreg screens		Utox and upreg screens
Mood and psychotic symptoms (VAS)	≥ 36 hours	Mood and psychotic symptoms (VAS)	≥ 36 hours	Mood and psychotic symptoms (VAS)
Interval discrimination		Interval discrimination		Interval discrimination
N-back test		N-back test		N-back test
Flanker		Flanker		Flanker
TMS - sham†		TMS - excitatory†		TMS - inhibitory†
Mood and psychotic symptoms (VAS)		Mood and psychotic symptoms (VAS)		Mood and psychotic symptoms (VAS)
Interval discrimination		Interval discrimination		Interval discrimination
N-back test		N-back test		N-back test
Flanker		Flanker		Flanker
Compensation: \$75		Compensation: \$50		Compensation: \$50 + \$25 completion bonus

*Scale also administered to healthy control participants. †Order of TMS randomized

Figure 3. Protocol B

Visit 4	Visit 5	Visit 6
NAART*		
PANSS		
YMRS		
MADRS		
PSYRATS-AH		
BRIEF-A*		
BIS-11*		
Fagerstrom*		
Utox and upreg screens	Utox and upreg screens	Utox and upreg screens
Mood and psychotic symptoms (VAS)	Mood and psychotic symptoms (VAS)	Mood and psychotic symptoms (VAS)
Finger tapping task	Finger tapping task	Finger tapping task
MSIT	MSIT	MSIT
TMS - sham†	TMS - excitatory†	TMS - inhibitory†
Mood and psychotic symptoms (VAS)	Mood and psychotic symptoms (VAS)	Mood and psychotic symptoms (VAS)
Finger tapping task	Finger tapping task	Finger tapping task
MSIT	MSIT	MSIT
Compensation: \$75	Compensation: \$50	Compensation: \$50 + \$25 completion bonus

*Scale also administered to healthy control participants. †Order of TMS randomized

Transcranial Magnetic Stimulation (TMS)

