• Protocol completion bonus	\$ 25
	TOTAL \$ 200

VI. BIOSTATISTICAL ANALYSIS:

A. Data variables being collected for the study (Data collection sheet)

We will collect the following data variables for this study:

Demographic information:

- Age
- Gender
- Race
- Ethnicity
- Handedness
- Education level
- Parental education level
- Clinical diagnosis
- Age at onset of illness
- Medications
- Past medical history
- Smoking habits
- Substance use/abuse history
- For female participants: first day of last menstrual period
- Results from urine screening for pregnancy and drug use

Scores from clinical scales:

- SCID (both patients and healthy controls)
- NAART (both patients and healthy controls)
- PANSS (patients only)
- YMRS (patients only)
- MADRS (patients only)
- PSYRATS (patients only)
- BRIEF-A (both patients and healthy controls)
- BIS-11 (both patients and healthy controls)
- Fagerstrom Test for Nicotine Dependence

Scores from subject-completed surveys and tasks:

- Visual Analogue Scales scores on mood and psychosis symptoms
- Interval discrimination task accuracy (Protocol A)
- N-back working memory task accuracy and reaction time (Protocol A)
- Flanker (Protocol A)
- Repetitive finger-tapping task accuracy (Protocol B)
- MSIT accuracy and reaction time (Protocol B)

B. Study endpoints

As this study is not a clinical trial, there is no particular outcome measure that will be indicative of a study endpoint. We will end the study when we meet our recruitment goals. In the event that we encounter any major adverse events, we will consult with the IRB to discuss whether the study needs to be terminated.

C. Statistical analysis

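### Protocol VI.C adjusts its patient-control change-score models for four scales collected only in patients, gives controls no value for them, and the SAP does not say whether those models still apply

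*Protocol*

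**What the plan says.** Protocol VI.C takes the change from before to after TMS at each visit and fits a two-way model to each outcome, with diagnosis (patient or control) and TMS type (three levels) as factors. It continues: "These models will include as covariates sex, age, handedness, medication load, and symptom severities". The severities are to be derived from NAART, PANSS, YMRS, MADRS, PSYRATS, BRIEF-A, BIS-11 and the Fagerstrom Test.

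Other sections show who receives each scale:

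- The data list in VI.A has entries that begin "PANSS (patients only" and "PSYRATS (patients only"; YMRS and MADRS carry the same mark.
- The visit lists in section V (Summary of Study Procedures) name those four scales for patients and omit them for controls.
- In Figures 2 and 3 the asterisk, explained as "Scale also administered to healthy control participants", stands only on NAART, BRIEF-A, BIS-11 and Fagerstrom.
- Section V, Clinical characterization, agrees: "The NAART, BRIEF-A, BIS-11, will be administered for all subjects", and "we will administer a Fagerstrom Test for Nicotine Dependence in all research participants".
- Medication is different. The same section records "medication information for all subjects during the first visit", and the control exclusions in section III include "Active use of neuropsychoactive medications".

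The SAP specifies mixed models for all outcomes except the visual analogue scales, and names TMS condition, time and their interaction as the terms of interest. It names neither diagnosis nor any of these covariates, and does not mention the VI.C model.

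**The concern.** VI.C is the only place in either document that sets out a model comparing TMS-induced change between patients and controls. As written, it needs four covariate values that no control will have. Neither document gives a floor value, an imputation rule, a nested coding or a composite score for controls, and neither states how missing covariates are handled. The complete-data rule in Protocol III concerns the three TMS visits, not covariates.

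The result therefore depends on a coding choice made later. One ordinary choice removes the whole control group and the patient-control comparison with it. Another keeps both, but changes what the diagnosis coefficient estimates. At stake is the use of the 50 controls planned for each of Protocols A and B in the change-score analysis.

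**Working it through.** The documents give no figure for this comparison. The power statement in VI.D concerns change within patients and is not an input here. The check is a count of rows and estimable terms.

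**Inputs.** 50 patients and 50 controls per protocol (Protocol III); three TMS types; one change score per participant and type, so 100 x 3 = 300 rows. The clinical scales are given once per protocol, at its first visit (Protocol V), so these covariates are constant within a person. Two readings of VI.C are needed: that the two-way model includes the interaction, which the text does not name, and that each of the eight scales enters separately, although scores derived from them could also mean a composite, which is not defined.

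**Columns.** Intercept 1 + diagnosis 1 + TMS 2 + diagnosis by TMS 2 = 6. Covariates: sex, age, handedness, medication load and eight scales = 12. Total 18.

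**Case 1: scores missing, incomplete rows deleted.** Only patients remain. The diagnosis column is constant and duplicates the intercept, and each of the two interaction columns duplicates its TMS column. Rank = 18 - 3 = 15. With main effects only there are 16 columns, rank 15, and one term (diagnosis) is lost.

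**Case 2: controls coded zero.** All 300 rows stay and the rank is 18 of 18.

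**Case 3: covariates measured in both groups only.** 6 design columns + 7 covariates (sex, age, handedness, NAART, BRIEF-A, BIS-11, Fagerstrom) = 13 columns, rank 13.

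| Handling | Patients + controls | Rows kept | Controls kept | Rank / columns |
|---|---|---|---|---|
| Missing, rows deleted | 50 + 50 | 150 of 300 | 0 | 15 / 18 |
| Missing, rows deleted | 40 + 40 (assumed) | 120 of 240 | 0 | 15 / 18 |
| Missing, rows deleted | 30 + 30 (assumed) | 90 of 180 | 0 | 15 / 18 |
| Coded zero | 50 + 50 | 300 of 300 | 50 | 18 / 18 |
| Both-group covariates | 50 + 50 | 300 of 300 | 50 | 13 / 13 |

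The smaller sizes are included because Protocol III expects fewer usable data sets than enrolled participants.

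**Precision of the TMS terms**, in units of the residual variance of a change score. Covariates that are constant within a person do not correlate with TMS type when all three visits are complete.

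- TMS contrast within patients: 1/50 + 1/50 = 0.040 in all three cases.
- Diagnosis by TMS contrast: 0.040 + 0.040 = 0.080 in cases 2 and 3; not estimable in case 1.

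**Diagnosis effect in case 2**, averaged over TMS types. With equal groups and one scale set to zero in controls, the variance inflation is 1 + 1/(2 CV²), where CV is the SD divided by the mean of the scale in patients. The documents give no CV. At an assumed CV of 1.0 this is 1 + 1/2 = 1.5; at 0.25 it is 1 + 16/2 = 9. VI.C lists four such scales. If they were uncorrelated with equal CV, the factor would be 1 + 4/(2 CV²), which is 3 at CV 1.0 and 33 at CV 0.25. This range shows only that the loss depends on unknown score distributions. The coefficient also becomes the difference between controls and a patient who scores zero on every one of these scales.

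**The case against.** The strongest reply is that little of importance is at risk. VI.D names change within the psychosis group as the main interest, and that is untouched. The explicit patient-control hypotheses in Aim 1 concern performance at baseline and after sham, which a change-score model would not test even when repaired. Zero coding rescues diagnosis by TMS at no cost. A fit that returned no controls and no diagnosis estimate would fail visibly, so a wrong published result is unlikely. The SAP may also have replaced VI.C altogether. All of this stands, and it limits the point to a repair of the patient-control model.

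It does not remove the point. VI.C states a covariate rule that cannot be run as written on both groups, and the choice that decides the outcome is unstated. Neither document says that the SAP model replaces VI.C. If it does, no stated model compares TMS effects between patients and controls, because the SAP names no diagnosis term.

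A reader might infer that the plan discards every control. The documents do not support that: deletion of incomplete rows is one possible handling and is nowhere specified. A reader might also put medication load in the same class. It is recorded for everyone and drops no one. It is expected to be near zero in controls because of the exclusion criterion, so it overlaps with diagnosis, but whether to keep it is a matter of judgement. The same kind of judgement applies to BRIEF-A, an executive-function inventory, since Aim 1 predicts executive dysfunction in patients.

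**Conclusion.** The concern holds in a limited form. Four of the eight severity scales in VI.C do not exist for controls, and no rule fills the gap. With the scores missing and incomplete rows deleted, 150 of 300 change scores and no controls remain. Diagnosis is lost, and so is diagnosis by TMS if the interaction is in the model (rank 15 of 18; 15 of 16 with main effects only). With zero coding, the TMS and diagnosis by TMS contrasts are intact, and only the diagnosis coefficient suffers, in meaning and in precision.

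These counts rest on 50 + 50 participants with complete three-visit data and on eight separately entered scales. The precision loss for diagnosis cannot be sized from the documents. The harm is confined to the patient-control comparison of change, and arises only if VI.C is still run.

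**What to change.** In VI.C, and in the SAP if diagnosis enters there:

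- In any model containing diagnosis, adjust only for covariates measured in both groups: sex, age, handedness and, if wanted, NAART, BRIEF-A, BIS-11 and Fagerstrom.
- Use PANSS, YMRS, MADRS and PSYRATS only in patient-only models.
- Medication load may stay or go; if it stays, note that it is expected to be near zero in controls.
- State whether the diagnosis by TMS interaction is included.
- State whether the SAP model replaces VI.C and, if so, which model compares patients with controls.

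A stated scoring rule for controls would also end the ambiguity. The text would then have to say that the diagnosis coefficient is a comparison with a patient at that score.

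The cost is a few sentences and no new data. The downside is that the patient-control comparison is not adjusted for symptom severity.
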